## 4. DATA ANALYSIS CONSIDERATIONS

All analyses will be conducted based on SAS 9.3 or higher.

All data in the database will be presented in by-patient data listings.

Unless otherwise stated, all listings will be sorted by study phase, treatment group, patient number, and assessment date (and time, if available). If assessment date is missing, chronological visit will be used for sorting.

Unless stated otherwise, continuous data will be summarized by treatment group based on number of patients (n), mean, median, standard deviation (SD), 25th percentile/first quartile (Q1), 75th percentile/third quartile (Q3), minimum value, and maximum value.

The geometric % coefficient of variation is calculated as  $100 * \sqrt{\exp(SD\log^2) - 1}$  where SDlog is standard deviation of log-transformed values.

Unless stated otherwise, categorical data will be summarized by treatment group using n and percentage based on the number of non-missing values.

- The number of missing values will be presented as a separate category with no percentage, but only if one or more patients are missing data.
- Counts of zero will be presented without percentages.

Statistics will be presented in the summary tables based on the following:

- Minimum and Maximum: same number of significant digits as the raw value
- Mean, Median, Q1, and Q3: one additional decimal place to that reported for Minimum and Maximum
- SD: two additional decimal places than presented for the Minimum and Maximum

Sponsor: Boston Pharmaceuticals, Inc.  
Protocol Number: BOS161721-02  
SAP Version and Date: Version 2.0, 29Nov2018

- Percentages: reported to one decimal place with the exception of 100% which will be displayed without decimals.
- P-values will be reported to four decimal places. If the value is below 0.0001 it will be noted as < 0.0001; if the value above 0.9999 it will be noted as > 0.9999.

Unless otherwise noted, statistical inference will be based on a 10% significance level (i.e. 90% confidence intervals will be produced).

Statistical testing will be performed on data from the Phase 2 study only.

All data up to the time of study completion/withdrawal from the study will be included in the analysis, regardless of duration of treatment.

Numbering for data displays will be based on ICH E3.

#### 4.1. Stratification and Covariates

The effects of noncompliance, background therapy use, treatment discontinuations, premature withdrawal from study and covariates will be assessed to determine the impact on the general applicability of results from this study. Exploratory analyses of the data may be conducted as deemed appropriate to evaluate factors for which analyses are not controlled.

Continuous efficacy endpoints will be assessed via analysis of variance (ANOVA) or analysis of covariance (ANCOVA) when applicable, adjusting for the baseline value.

#### 4.2. Evaluation of Subgroups

There are no formal plans for examining subgroups.

#### 4.3. Multiple Comparisons and Multiplicity

The Type 1 error rate will not be adjusted for multiplicity.

### 5. GENERAL DATA HANDLING CONVENTIONS

#### 5.1. Assigned and Actual Treatment

Patients are assigned to a study treatment and cohort based on the study schematic in Section 3.

Full analysis set (FAS) and per protocol (PP) analyses will be conducted on the basis of the randomized (assigned) treatment. Safety analyses will be conducted on the basis of the actual treatment received based on the exposure data collected in the case report form (CRF).

## 5.2. Reference Dates

- Screening date is defined as the CRF provided date on which a patient was screened for trial entry.
- Randomization date is defined as the date on which the patient is randomized to study treatment.
- Treatment start date is defined as the date of first dose of study drug.
- Treatment end date is defined as the date of last dose of study drug.
- Age will not be calculated and will come directly from the CRF. The CRF uses the informed consent date as its reference date for age calculation.
- Safety data, such as AEs and laboratory assessments will use the treatment start date as a reference date.
- Efficacy data will use the randomization date as a reference date.
- Study day will be based on treatment start date as a reference date.

## 5.3. Study Day and Duration Variables

Reference date calculations will be defined as follows, assuming non-missing dates:

- date of interest – reference date + 1 when the date of interest is on or after the reference date;
- otherwise, date of interest – reference date.

If either date is missing or incomplete, reference date calculations will not be performed. Date imputation will be performed as identified in Section 5.6.

Study day will either have a negative value if collected before dosing or a positive value if collected on or after the day of drug dosing; there will be no study day zero.

Duration of time is dependent on reference dates and will be calculated in a manner similar to that of the reference date calculation. Duration on study is defined as the end of study date – randomization date + 1. Duration of treatment is defined as treatment end date – treatment start date + 1, where treatment end date is the date of last dose of study drug.

Time-to-event endpoints are followed until first event or censoring. As a result, event time will be calculated as: event or censoring date – reference date + 1. These are further described in Section 7.

When reporting time-to-event data (Time to Medication Failure, Time to first SRI-4 Response, Time to BILAG A Flare or >1 BILAG B flare) or duration outcomes, the results (in days) above will be converted to an appropriate unit. When reporting in months it will be divided by 30.4375; for reporting in weeks it will be divided by 7; and for reporting in years it will be divided by 365.25.

#### 5.4. Study Time Periods

Where applicable, data reporting will be classified by the following study periods for analysis:

- Pre-treatment is defined as the period prior to a patient's treatment start date.
- On-treatment is defined as the period between a patient's treatment start date and treatment end date, inclusive.
- Post-treatment is defined as the period of time following the on-treatment period.

#### 5.5. Baseline, Post-Baseline Changes, and Last Observation Carried Forward (LOCF)

Unless stated otherwise, baseline and post-baseline change values will be based on the following:

- Baseline will be based on the last non-missing value collected prior to or on the treatment start date (and time, if applicable).
- Post-baseline values will be those collected after the date/time of first dose of study drug.
- Change from baseline is defined as: value – baseline value.
- Most extreme change: The maximum most extreme change will be the maximum post-baseline value; the minimum most extreme change will be the smallest post-baseline value. This calculation will consider all assessments collected after the first dose of study drug, scheduled or unscheduled.

LOCF will be based on the last non-missing value collected. This calculation will consider all assessments, scheduled or unscheduled, including baseline. If a patient withdraws from the study, their most recent non-missing assessment prior to withdraw will be carried forward. Additional details regarding LOCF for specific endpoints are provided in Section 7.

Observed values do not incorporate any imputations and are presented as collected.

#### 5.6. Imputation of Partial Dates

##### **Adverse Events**

- If the AE start date is completely missing, or if the patient was not treated, no imputation will be conducted.
- If the AE start date is missing day and month, do the following:
  - If the treatment start date is missing or the AE start year does not fall in the same year as that of the treatment start date or if the AE record contains information to indicate that the event ended before the treatment start date (e.g. the AE end date month and year are earlier than the treatment start date or the full AE end date is

known and occurs earlier than the treatment start date), then set the AE start month and day to January 1st.

- Otherwise, set the AE start date to the treatment start date.
- If only the AE start day is missing, do the following:
  - If the study treatment start date is missing or the AE start month and year does not fall in the same month/year as that of the treatment start date or if the AE contains information to indicate that the event ended before the treatment start date, then set the AE start month and day to the 1st day of the month of the treatment start date.
  - Otherwise, set the AE start date to the treatment start date.
- AE end dates will not be imputed.

### **Prior, Concomitant, and Subsequent Medications**

- The imputation rules for AE start dates will be used for medication start dates.
- Medication stop dates will be imputed as follows:
  - If the stop date is only missing the day, then the stop day is the last day of the month
  - If the stop date is missing both the day and month and the year matches the last study date, then the stop month and day is the earlier of the last study date and December 31
  - If the stop date is missing both the day and month and the year is earlier than the last study date, then the stop month and day is December 31
  - If the stop date is completely missing, no imputation is performed, and the medication will be classified as a concomitant medication for subjects who were treated unless the medication began after the end of study treatment.

### **5.7. Multiple Assessments and Visit Windows**

Nominal visits (e.g. those identified by the study CRF) will be the basis of summarization and statistical analysis; no visit date windowing will be conducted. Unscheduled data may be included in summaries of most extreme, baseline, and endpoint values; summaries of specific abnormalities any time post-baseline; and patient data listings

### **5.8. Treatment Group Display**

Treatment groups will be displayed with the following columns. See the mock shells for additional details and a visual representation of the treatment group display.

- Phase 1b MAD: Cohort 1 BOS 20mg
- Phase 1b MAD: Cohort 2 BOS 60mg
- Phase 1b MAD: Cohort 3 BOS 120mg
- Phase 1b MAD: Placebo

- Phase 1b MAD: Total BOS (All patients treated with BOS161721, excludes placebo)
- Phase 2 POC: BOS <dose> where <dose> is the value determined during the IA
- Phase 2 POC. Placebo
- Overall: Total BOS <dose>mg where <dose> is the common dose between the Phase 1b MAD and Phase 2 POC portions of the study (to be determined during the IA). If a common dose is not determined, this column will be omitted.
- Overall: Total BOS (Patients treated with BOS161721 in MAD and POC, excludes placebo)
- Overall: Total Placebo (Placebo patients in MAD and POC, excludes patients treated with BOS161721)

## 5.9. Missing Data

Missing data imputation for the efficacy endpoints are discussed in the corresponding efficacy sections. AE and concomitant medication date imputations are described in Section 5.6. Missing data for noncompartmental analysis of pharmacokinetics will follow standard imputation methods, as described in a separate Clinical Pharmacology Analysis Plan (CPAP). Otherwise, missing data will not be imputed.

# 6. STUDY PATIENT DATA

## 6.1. Analysis Populations/Sets

Full Analysis Set (FAS): Defined as all patients who receive at least one dose of study treatment and have at least one evaluable post-baseline efficacy evaluation (BILAG, PGA, SLEDAI-2K, CLASI, ACR-28, SLICC/ACR, CCI, or CCI). FAS analyses will be conducted on the basis of the randomized treatment. The FAS will be used as the basis for the primary efficacy analysis.

Safety Analysis Set (SS): Defined as all patients who receive at least one dose of study treatment. Safety analyses will be conducted on the basis of actual treatment received. The SS will be the basis of all safety reporting.

Per Protocol Set (PP): Defined to exclude major protocol violations from the efficacy analysis. The PP will include all patients from the FAS except those with major violations to the protocol deemed to impact the analysis of the primary endpoint. These violations will be identified based on blinded data prior to study unblinding. PP analyses will be conducted on the basis of the randomized treatment. Additional information on inclusion into this population can be found in Section 6.3.

Pharmacokinetic Analysis Set (PK): Defined as the FAS patients who received at least one dose of BOS161721 with sufficient concentration data for the calculation of at least one PK parameter.

## 6.2. Patient Disposition

Disposition data will be summarized for all randomized patients. The number of patients in each analysis population, the number of patients who discontinued study treatment including reasons, and the number of patients who discontinued the study including reasons will be summarized. The number of patients who completed the study will also be summarized. Data will be presented by study phase and treatment group.

A by-patient listing of patient disposition data including reason for discontinuation, if applicable, will be presented for all randomized patients. A by-patient listing of randomization details will also be provided for all randomized patients.

A by-patient listing of inclusion/exclusion criteria and screen failures will be produced for all enrolled patients. Screen failures will otherwise not be included in any analyses.

## 6.3. Protocol Deviations

Protocol deviations will be identified and classified as major violations before database lock and unblinding. Major protocol deviations may include but are not limited to:

- Violation of Inclusion/Exclusion Criteria
- Use of prohibited therapies
- Incorrect treatment

Protocol deviations will be summarized by protocol version, deviation category, and major/minor designation. Protocol deviations will be summarized by study phase and treatment group for all randomized patients.

A listing of protocol deviations will be provided for all randomized patients.

## 6.4. Demographic and Baseline Characteristics

Patient demographics and baseline characteristics will be summarized in the SS. These will include age (years), gender (Male / Female), ethnicity (Hispanic or Latino / Not Hispanic or Latino), race (American Indian or Alaska Native / Asian / Black or African American / Native Hawaiian or Pacific Islander / White / Other), baseline height (cm), baseline weight (kg), and baseline BMI (kg/m^2). Age is reported as collected in the clinical database and will also be categorized as a categorical variable ( $\leq 45$ ,  $> 45$ - $< 65$ ,  $\geq 65$ ) for reporting. Patient eligibility for central review will be summarized. Childbearing potential and birth control methods for female and male patients will be summarized for the DMC meetings and interim analysis only. Demographics and baseline characteristics will be summarized by study phase and treatment group.

Sponsor: Boston Pharmaceuticals, Inc.  
Protocol Number: BOS161721-02  
SAP Version and Date: Version 2.0, 29Nov2018

Demographics and baseline characteristics will be listed for all randomized patients. A separate by-patient listing will be created for childbearing potential and birth control for all randomized patients.

The following conversions and equations will be used as applicable:

Height (in cm) = height (in inches) \* 2.54

Weight (in kg) = weight (in lbs) \* 0.4536

BMI (kg/m^2) = weight(kg)/[height(m)]

## 6.5. Medical History

Medical history will be presented in data listings for all randomized patients. Medical history coded terms will be provided, including the system organ class and preferred term. The data management plan specifies the version of MedDRA used for medical history coding.

## 6.6. Prior and Concomitant Medication and Procedures

The incidence of medication use will be summarized by WHO Drug Dictionary anatomic therapeutic class (ATC) Level 2 classification (i.e. therapeutic main group) and preferred name. A patient will be counted only once at each level of reporting. Prior medications are those which have been identified to have been discontinued prior to the first dose of study medication. Concomitant medications are those which have been identified to have been taken at any point during the period of time between the first and last dose of study medication, including medications which started prior to first dose of study medication but are ongoing at first dose. Subsequent medications are those which have been started after the last dose date. The data management plan specifies the version of WHO Drug used.

Partial dates will be imputed according to Section 5.6 for the determination of prior, concomitant, and subsequent medications.

Concomitant medication use will be summarized and presented by study phase and treatment group in the SS.

All prior and concomitant medication data will be provided together in a by-patient listing including the verbatim and preferred drug name and WHO ATC Class (ATC Level 2) for all randomized patients. Past biological, immunosuppressant, antimalarial and corticosteroid SLE medication history data will be listed separately for all randomized patients.

Concomitant procedures will be presented in a data listing for all randomized patients.

## 6.7. Study Drug Exposure and Compliance

The total dose administered (mL) and the number of doses received will be summarized as continuous variables. The number and percentage of patients dosed and the number of patients who received the total planned dose at each nominal, protocol specified, visit (Day 0 / Day 30 / Day 60 / Day 90 / Day 120 / Day 150 / Day 180) will be summarized. The denominator for the number of patients dosed will be the number of patients in the SS. The denominator for the number of patients who received the total planned dose will be the number of patients dosed at the corresponding nominal visit.

The percent compliance will be calculated descriptively and is defined as 100 \* (total actual dose summed across all visits)/total planned dose summed across all visits).

The duration of exposure in days will also be summarized descriptively and is defined as the last dose date – first dose date +1.

Study drug exposure and compliance will be presented by study phase and treatment group in the SS.

By-patient listings of BOS161721 and placebo dosing data will be produced for all patients in the SS.

## 7. EFFICACY

### 7.1. Primary Efficacy Endpoint and Analyses

Safety is the primary endpoint for the Phase 1b MAD portion of the study and is discussed in Section 9. Efficacy will be evaluated for the Phase 1b MAD portion of the study as an exploratory endpoint and details will be included in relation to the Phase 2 POC portion of the study within this section.

#### 7.1.1. The proportion of patients with a SRI-4 response at Day 210

The primary efficacy endpoint is the proportion of patients who achieve a SRI-4 response at Day 210.

The SRI-4 is a composite index of SLE disease improvement that consists of scores derived from the SLEDAI-2K and the BILAG 2004 Index. Response based on the SRI-4 is defined by:

1)  $\geq$  4-point reduction from baseline in SLEDAI-2K global score

AND

Sponsor: Boston Pharmaceuticals, Inc.  
Protocol Number: BOS161721-02  
SAP Version and Date: Version 2.0, 29Nov2018

2) No new severe disease activity (BILAG A organ score) or more than 1 new moderate organ score (BILAG B) compared with baseline

AND

3) No deterioration from baseline in the PGA by  $\geq 30\text{mm}$ .

The proportion of patients who achieve a SRI-4 response at Day 210 will be presented and assessed using Pearson's chi-square test. The number of SRI-4 responders, treatment difference versus placebo, odds ratio, and 90% confidence interval will be displayed. The 90% confidence interval will be calculated with Wilson (score) confidence limits for the binomial proportion by treatment group. If any of the expected cell counts are less than 5, Fisher's exact test will be used and exact confidence intervals will be constructed. The analyses will be repeated for each of the three components contributing to the SRI-4 response. The primary analysis of the primary efficacy endpoint will be performed in the FAS and presented by treatment group. The analysis will be repeated in the PP analysis set.

The superiority of BOS161721 relative to placebo will be evaluated. If the proportion of SRI-4 responders for the selected POC dose in BOS161721 arm is higher than that of the placebo arm, then BOS161721 will be considered superior to placebo if the 2-sided p-value is less than 0.10.

#### **Evaluability/Non-Responders:**

Patients who received prohibited medications or unallowable corticosteroid (CS) usage will be considered "medication failures" and will be treated as non-responders for the primary efficacy analysis. Prohibited medications are detailed in Appendix 4 of the study protocol. Prohibited medications and unallowable CS usage will be recorded as protocol deviations in the clinical database.

A patient is considered to have unallowable CS usage if any of the following is not met:

- After Day 0 (after initiation of study therapy), no up-titration above 10 mg/day is allowed except for up to 1 CS burst for increased disease activity.
- Tapering is allowed after randomization except within 60 days of the primary (Day 210) and secondary (Day 120) endpoint assessments. Between Day 60 and Day 120, and between Day 150 and Day 210, oral CS doses must be held constant.
- A maximum of 1 oral CS "burst" for increased SLE disease activity will be allowed during the study between Day 0 and Day 60, according to the following:
  - An oral CS "burst" between Day 0 and Day 60; (an increase of  $\leq 40\text{ mg/day}$  of prednisone or equivalent), which must be tapered down to a maximum of 10 mg/day within 2 weeks of initiation of the "burst"

- Alternatively, a single intramuscular (IM) dose of methylprednisolone (40 mg or equivalent) is permitted
- The course of the oral CS “burst” is not permitted to extend beyond Day 60

Patients who received an allowable CS burst but having missing data at Day 210 will be considered a medication failure and will be treated as non-responders for the primary efficacy analysis. The determination of medication failures will be reviewed using blinded data and finalized prior to unblinding. Once a patient is determined to be a non-responder, they will not be considered for response at a later visit.

If a patient has a BILAG, SLEDAI-2K, or PGA assessment outside of a 30 day +/-4 day window since the previous assessment (0-25 or >=35 days since the prior assessment), the corresponding result will be considered not evaluable and will be excluded from all analyses. The excluded result will not contribute to LOCF analyses. In these cases, the individual assessment (i.e. BILAG, SLEDAI-2K, or PGA) will be considered as if it was missed and analyses will be handled per the below details.

#### **Missing Data:**

- If a patient is missing data during the pre-treatment period for SLEDAI-2K, PGA, or BILAG, the patient will be excluded from the primary efficacy analysis.
- Missing data at Day 210 for overall components for SLEDAI-2K, BILAG, and PGA will be addressed by employing a last observation carried forward (LOCF) analysis within each overall component as described in Section 5.5. For example, if a patient has data for SLEDAI-2K and BILAG at Day 210 but is missing PGA at Day 210, the PGA component would employ LOCF. Data collection and scoring will be performed in the clinical database for BILAG, SLEDAI-2K, and PGA. As such, missing individual items contributing to any of the overall components will not be imputed/carried forward.
- Missing data for visits other than Day 210 will be handled in the same way as Day 210.
- If one or more consecutive visits are missed, LOCF analyses will be carried forward from the most recent prior assessment. For example, if the Day 150, Day 180 and Day 210 assessments are all missed but the Day 120 assessment was performed, the Day 120 assessment would be carried forward to Days 150, 180, and 210 for analysis.

Several sensitivity analyses will be performed:

| Analysis        | Criteria   |
|------------------------|---|
| Sensitivity Analysis 1 | A sensitivity analysis of the primary efficacy endpoint will be performed (including LOCF methods) for patients in the full analysis set excluding patients with: |

|                        |  |
|------------------------|--|
|                        | 
(1) Positive anti-drug antibodies at baseline through Day 210.
AND
(2) Confirmed nAb at Day 90 and Day 180 OR missing Day 90 and missing Day 180 nAb OR missing Day 90 nAb and confirmed nAb at Day 180.
 
Missing ADA and missing nAb results will be handled with a LOCF approach as discussed in Section 5.5. Additional analyses exploring impact of baseline factors such as baseline disease severity, race, and other characteristics may be performed.
   |
| Sensitivity Analysis 2 | A sensitivity analysis of the primary efficacy endpoint will be performed (including LOCF methods) for patients in the full analysis set; however, if a patient has a BILAG, SLEDAI-2K, or PGA assessment outside of a 30 day +/- 4 day window since the previous assessment (0-25 or >=35 days since the prior assessment), the corresponding result will be considered evaluable and will be included in the analysis and will contribute to LOCF.   |
| Sensitivity Analysis 3 | A sensitivity analysis of the primary efficacy endpoint will be performed (excluding LOCF methods) to consider the effect of missing data by excluding patients with either or both of the following criteria:
(1) Missing assessments at Day 210 (patients with a missed assessment of any of BILAG, SLEDAI-2K, or PGA at Day 210 would be excluded).
AND/OR
(2) Patients with any Day 210 assessment which occurred outside of the 30 day +/- 4 day window (patients with an out of window assessment of any of BILAG, SLEDAI-2K, or PGA at Day 210 would be excluded). |

Additional sensitivity analyses may be performed to consider the effect of missing data.

Statistical testing data will be omitted from MAD Phase 1b treatment group displays.

A summary of disposition of SRI-4 response at day 210 will be presented by study phase and treatment group in the FAS and PP. Sensitivity analysis 1 will also be performed for disposition of SRI-4 response at day 210. These summaries will include the number of SRI-4 responders and the number of SRI-4 non-responders with a breakdown of reasons for non-response (early withdrawal, medication failure, <4-point reduction from baseline in SLEDAI-2K global score, new BILAG 1A/2B, and PGA worsening). Denominators for percentages will be the number of patients eligible for SRI-4 response analysis.

Sponsor: Boston Pharmaceuticals, Inc.  
Protocol Number: BOS161721-02  
SAP Version and Date: Version 2.0, 29Nov2018

A listing of SRI Response data at Day 150, Day 180, and Day 210 will be presented in the FAS. A listing of patients excluded from the efficacy analysis will also be provided for all randomized patients.

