### 3.3. Sample Size Considerations

Sample size in the Phase 1b MAD part of the study is based on operational consideration.

The sample size in the Phase 2 POC study is based on the primary endpoint, SRI-4 Response at Day 210. Approximately 156 additional patients will be randomized in a 2:1 ratio to BOS161721 versus placebo to achieve 132 evaluable patients in the FAS. This assumes 24 patients will drop prior to having received treatment and an evaluable post-baseline efficacy measure. Enrollment and randomization will be monitored in a blinded fashion and increased if needed to ensure at least 132 patients are randomized into the FAS.

A total of 132 patients randomized provides more than 80% power to detect a treatment difference of 25% in SRI-4 response rates at Day 210, based on a targeted 2-sided significance level of 10% and using a 2-sided Pearson's chi-squared test. This assumes a response rate of 65% for BOS161721 and 40% for placebo, where missing data at Day 210 is carried forward

Sponsor: Boston Pharmaceuticals, Inc.  
Protocol Number: BOS161721-02  
SAP Version and Date: Version 2.0, 29Nov2018

from most recent non-missing result and patients are treated as a non-responder if a prohibited medication defined as a medication failure occurs.

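### SAP v2.0 carries withdrawn patients' last SRI-4 components forward to Day 210 without limit, and no listed sensitivity analysis counts withdrawal as failure

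*SAP*

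**What the plan says.** The text below is SAP v2.0 (29 Nov 2018); v1.0 has the same rules.

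- **Section 7.1.1, Missing Data.** "Missing data at Day 210 for overall components for SLEDAI-2K, BILAG, and PGA will be addressed by employing a last observation carried forward (LOCF"), component by component, as described in Section 5.5. The worked example for consecutive missed visits has no limit on span: "the Day 120 assessment would be carried forward to Days 150, 180, and 210 for analysis".
- **Section 5.5.** "If a patient withdraws from the study, their most recent non-missing assessment prior to withdraw will be carried forward".
- **Section 7.1.1, Evaluability/Non-Responders.** Prohibited medication or unallowable steroid use makes a patient a medication failure and a non-responder. One further group is added: "Patients who received an allowable CS burst but having missing data at Day 210 will be considered a medication failure".
- **Section 7.1.1, disposition of Day 210 response.** Non-responders are tabulated with a "breakdown of reasons for non-response (early withdrawal, medication failure", followed by failure on each of the three SRI-4 components).
- **Section 7.1.1, sensitivity analyses.** Analyses 1 and 2 include LOCF. In Analysis 3, "patients with a missed assessment of any of BILAG, SLEDAI-2K, or PGA at Day 210 would be excluded".
- **Section 3.3.** The design assumes 65% against 40% response, with missing Day 210 data carried forward, "based on a targeted 2-sided significance level of 10% and using a 2-sided Pearson's chi-squared test".

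**The concern.** The objective is superiority on SRI-4 response at Day 210. For a patient who has left, the rule substitutes response at the last usable visit, however long ago that was. A patient who stops at Day 60 while meeting the three criteria is scored as a success 150 days later.

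The planned tables do not show how much the result depends on this. The disposition summary treats early withdrawal as a category of non-response, but nothing in the plan makes withdrawal a non-response or ranks the reasons. Two programmers could place the same withdrawn patient differently in the primary analysis and in that table. The listed sensitivity analyses either repeat the carry-forward or remove these patients. Superiority rests on one proportion tested at two-sided 0.10, so a few patients classified by convention could affect the conclusion.

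**Working it through.** **1. Following the rules for one patient.** A patient withdraws at Day 60 meeting all three criteria, with no medication failure and no burst.

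| Rule (v2.0) | Result |
|---|---|
| 7.1.1 Missing Data with 5.5 | Day 60 components carried to Day 210: responder |
| 7.1.1 Non-Responders | Not a medication failure: stays a responder |
| Disposition summary | Early withdrawal exists as a reason for non-response; no rule says whether it applies |
| Sensitivity Analyses 1 and 2 | LOCF kept (unless the Analysis 1 antibody criteria exclude the patient): responder |
| Sensitivity Analysis 3 | Excluded |

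The carry-forward is not universal. Medication failures and burst patients with missing Day 210 data are non-responders. A patient with only baseline to carry cannot show the 4-point SLEDAI-2K drop. The visit-window exclusion in 7.1.1 can also discard an assessment made soon after a visit, so that an older one is carried.

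**2. The plan's own figure.** With 88 and 44 patients (132 at 2:1), 65% against 40% and two-sided alpha 0.10, the pooled rate is (57.2 + 17.6)/132 = 0.567. The null standard error is sqrt(0.2456 × (1/88 + 1/44)) = 0.0915. The alternative standard error is sqrt(0.2275/88 + 0.24/44) = 0.0897. Then z = (0.25 − 1.645 × 0.0915)/0.0897 = 1.11, so power is 86.6%. Exact enumeration gives 86.3%. The stated power of more than 80% reproduces, with carry-forward as its premise. The 24 of 156 patients allowed for are lost before entering the FAS, so they say nothing about later withdrawal.

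**3. Gap between the two ways of handling withdrawal.** LOCF difference minus non-response difference = w_A × r_A − w_P × r_P, where w is the share withdrawing and r the share of withdrawers responding when last seen. The SAP gives neither, so all inputs are assumed.

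| w active/placebo | r active/placebo | Gap, points | Share of 25 |
|---|---|---|---|
| 15%/15% | 50%/30% | 7.5 − 4.5 = +3.0 | 12% |
| 15%/10% | 50%/30% | 7.5 − 3.0 = +4.5 | 18% |
| 20%/10% | 50%/30% | 10.0 − 3.0 = +7.0 | 28% |
| 10%/20% | 50%/30% | 5.0 − 6.0 = −1.0 | −4% |
| 10%/20% | 30%/30% | 3.0 − 6.0 = −3.0 | −12% |

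The last row changes the responder shares as well as the withdrawal rates, so compare it with the others with that in mind.

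**4. Effect on the test.** Suppose the arms are equal (35% or 40%) when withdrawal counts as failure, active withdrawal is 10 points higher (15% against 5%, or 20% against 10%), and 40% to 60% of withdrawers were responding when last seen. LOCF then shows a 4 to 6 point difference, and the chance of declaring superiority rises from about 4.9% to about 11% to 16%.

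**5. Power if withdrawal becomes non-response.** Take 65%/40% as the LOCF rates and let withdrawers respond at their arm's rate, so each rate becomes p × (1 − w).

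| w active/placebo | Rates | Power |
|---|---|---|
| 10%/10% | 58.5%/36.0% | 79% |
| 15%/15% | 55.3%/34.0% | 75% |
| 20%/20% | 52.0%/32.0% | 71% |
| 20%/10% | 52.0%/36.0% | 54% |
| 10%/20% | 58.5%/32.0% | 90% |

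If withdrawers respond at half their arm's rate, equal withdrawal of 10% to 20% gives 83% to 79%.

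**The case against.** **The text is superseded.** v3.0 (13 Nov 2020) is the current plan, and its Sections 5.5 and 7.1.1 are not shown. Its Section 11 says the LOCF rules were further detailed, and its Appendix 13.1 mentions LOCF as a possible sensitivity analysis, which would be odd if LOCF were still primary. On the other hand, v3.0 Section 7.2.12.1 still switches LOCF off when it borrows the methods of 7.1.1. The retained rule is therefore unknown. This stands, and it makes the fix conditional.

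**The table need not contradict the analysis.** A reader might infer that the disposition table already treats every withdrawal as non-response. It does not say so: it breaks down reasons among non-responders and can be read as labelling only withdrawers who fail under LOCF. That reading is fair, but such patients also fail an SRI-4 component, so it needs a ranking of reasons that the plan does not give. What remains is an unreconciled gap, not two opposite rules. The burst rule is likewise a stated exception to LOCF, not a contradiction.

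**The plan does consider withdrawal.** Section 4.1 says the effects of premature withdrawal will be assessed, and 7.1.1 allows further sensitivity analyses for missing data. Comparing the primary result with Analysis 3 also shows something. None of this specifies an analysis with withdrawal as failure.

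**LOCF matched the sizing.** Section 3.3 built 65%/40% on carry-forward, so changing the primary rule carries a real price in power. This stands.

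**Conclusion.** The point holds for v2.0 and v1.0: as written, an early leaver can be scored as a Day 210 responder, the disposition table has no rule tying it to that result, and no listed analysis tests withdrawal as failure.

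A reader might go further and infer that LOCF inflates the drug effect. The documents do not support that. The direction depends on which arm withdraws more and in what state, and when placebo withdraws more, counting withdrawal as failure can favour the drug more than LOCF does. The gap of about −3 to +7 points and the 11% to 16% error rate are illustrations under assumed rates, not estimates for this trial. Nor can it be claimed that the current v3.0 has this defect; that depends on a section not shown.

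**What to change.** First confirm what v3.0 Section 7.1.1 says. If the v2.0 rule is retained:

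- Pre-specify an analysis of the primary endpoint in which withdrawal before Day 210 is non-response and LOCF is limited to intermittently missing components in patients still on study.
- Add a tipping-point analysis alongside Sensitivity Analysis 3.
- Make each disposition table use the same withdrawal rule as the analysis it describes, with a stated order of reasons.

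This costs SAP wording and a few tables, and can leave the primary analysis and the sizing as they are. If the sponsor instead makes non-response the primary rule, full LOCF should stay as a sensitivity analysis and Section 3.3 must be restated, because both 65%/40% and the claim of more than 80% power assume carry-forward. The power figures above show that the claim may then fail, more so if active patients withdraw more often.
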